##### 9.4.3.1.1 At the time of enrolment

If the blood smear collected two weeks after cohort enrolment (parasite clearance) visit is negative, person-time accrual will begin two weeks after enrolment to account for the post-prophylactic effect of the full treatment course with artemether-lumefantrine

##### 9.4.3.1.2 After a positive RDT and malaria treatment

Similarly, two weeks of person-time will be subtracted after each treatment provided during the follow-up. This scenario would result in an event in the numerator

##### 9.4.3.1.3 Visit following a positive malaria treatment

At the next visit (one month later), if the participant fulfils the criteria for clinical malaria (mRDT positive with symptoms), he/she will again be treated, and two weeks of person-time will be

removed. However, this will only be counted as an event (i.e. contribute to the numerator) if subsequent PCR testing for *P. falciparum* in the laboratory is positive. The rationale for this is based on the long tail of histidine-rich protein-2 (HRP2) antigenemia which can persist for weeks after active infections have cleared, resulting in false-positive mRDT results.

9.4.3.1.4 Visit where participant’s overnight sleeping outside of the cluster of residence is documented

If a person sleeps outside of their cluster of residence for a period to be defined in the Statistical Analysis Plan based on a consensus between the three trials in Kenya (this protocol), Zambia and Mali, person-time and events for that month will be excluded. If the participant is found to be RDT positive, this event will not count in the numerator

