## 5 OBJECTIVES AND OUTCOMES

Table 1: Objectives and outcomes

5.1 PRIMARY OBJECTIVE AND OUTCOME	
Primary objective	Primary endpoint
To determine if ATSB deployment plus universal LLIN coverage is superior to universal LLIN coverage alone in reducing the case burden of clinical malaria in western Kenya	
 
The incidence rate of clinical malaria by the end of year-2, defined as current fever (axillary temperature of <math>\geq 37.5^{\circ}\text{C}</math>) or history of fever in last 48 hours and a positive rapid diagnostic test (RDT, pLDH or HRP2), in children aged 1-<15 years enrolled in the cohort study
 

5.2 SECONDARY OBJECTIVES AND OUTCOMES	
5.2.1 Efficacy	
Secondary objectives	Secondary endpoints
To determine if ATSB deployment plus universal LLIN coverage compared to universal LLIN coverage alone is superior in reducing malaria infection	
 
The time to first malaria infection assessed by PCR by the end of year-2, in children aged 1-<15 years enrolled in a cohort study
 
The incidence rate of malaria infection detected by RDT (pLDH) by the end of year-2, in children aged 1-<15 years enrolled in a cohort study
 
The prevalence of malaria infection diagnosed by RDT in continuous household surveys in participants aged <math>\geq 1</math> month.
 

To determine in ATSB deployment plus universal LLIN coverage compared to universal LLIN coverage alone reduces the clinical case burden in health facilities and communities	
 
The incidence rate of RDT or microscopy confirmed clinical malaria assessed through passive surveillance at health facilities and community-based surveillance by Community Health Volunteers serving the village-clusters
 

To determine if the rate of overall illness events differs in the ATSB deployment plus universal LLIN coverage arm when compared to the control arm	
 
The incidence rate of non-malaria illness in the cohort study
 
The incidence rate of all-cause sick visits assessed through passive surveillance at health facilities and community-based surveillance by community health volunteers
 

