#### 6.3.3.1 Cohort study (active case detection)

Participants aged 1 to <15 years who are usual residents of households within a core area of a study cluster will be randomly selected for enrolment into an active cohort (see section 9.1.2, Cohort study to assess the incidence of clinical malaria, page 34). All consented and enrolled cohort members will be given a presumptive treatment course of artemether-lumefantrine to clear any malaria infections. Parasite clearance will be confirmed two weeks after treatment. The scheduled monthly cohort visits will begin one month after the first day of this treatment. During monthly visits, study staff will collect a fingerprick (or heel prick in small infants) blood sample (about 250uL to 1 ml) for dried blood spots on filter paper. Should the cohort member report a fever in the last 48 hours or have an axillary temperature of  $\geq 37.5^{\circ}\text{C}$  at the time of the visit, the study staff member will perform a malaria RDT, and if positive, will treat the participant as per the Kenya Ministry of Health guidelines. A questionnaire will be administered to all cohort members and/or their caregivers to assess for illness, care-seeking, and LLIN usage, among other indicators. Several questions will be asked to monitor for any SAEs. A questionnaire assessing ATSB knowledge, attitudes and perceptions (KAP) will also be administered. Please see section 9.1.7, Rapid ethnographic methods, page 39, for more details.

Figure 4: Overview of activities and procedures in intervention and control areas

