##### 9.1.2.1 *At recruitment/enrolment*

- Informed consent will be administered to the parent/caregiver, and assent to the participant if he/she is 13-<15 years of age
- A fingerprick blood sample (~250µL or 1mL) will be collected to perform an RDT and to prepare approximately five dried blood spots (DBS) on filter paper for subsequent molecular and potentially serological testing and for evaluation of mosquito salivary antigens
- All cohort members will be treated with artemether-lumefantrine (AL; first-line antimalarial in Kenya) irrespective of their RDT result to clear any subpatent infections that may exist
- A questionnaire will be administered to the head of the household to assess household assets for the construction of socio-economic status (SES) categories and to assess household malaria control measures (e.g. number of LLINs, housing construction)
- A questionnaire will be administered to the parent/caregiver and/or the participant to assess activities of interest, including medical and vaccination history, medication use, inclusion in other clinical trials, care-seeking behaviour, LLIN use, daily commuting and travel information, and information about the structure that the participant sleeps in
  - A photograph will be taken of vaccination history and pertinent medical records from the maternal child health booklet or other records

- For participants enrolled in the HDSS or clinical studies, we will link the cohort data to their study/HDSS records
- For young women of childbearing age (12-14 years), pregnancy status will be evaluated in a private and confidential location through the following algorithm:
  - If the woman has had menarche, her last menstrual period was  $\geq 6$  weeks ago, and if she has any suspicion that she may be pregnant, then she will be offered a urine pregnancy test
  - If she declines or is found to be pregnant, she will be considered ineligible for the cohort
- A photograph may be taken of the participant to create a study identification badge that the participant will keep for identification by study staff for scheduled and sick visits

9.1.2.2 *Parasite clearance confirmation visit (2 weeks after enrolment)*

- Before this visit, the study team will call the cohort member to remind them of the upcoming visit and reschedule if necessary. Up to three visit attempts will be made to complete the parasite clearance confirmation visit.

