- Two weeks after the enrolment visit, the household will be visited and a finger-prick blood sample (~250 $\mu$ L to 1mL) will be drawn to prepare five dried blood spots, and to prepare a blood smear for parasite clearance confirmation.
- If the participant is febrile at this visit, the staff member will review the RDT result from the enrolment visit.
  - If the enrolment visit RDT was negative, the participant will be re-tested with an RDT and if positive, the participant will be ineligible for the cohort and second-line antimalarial treatment will be administered as per national guidelines (e.g. dihydroartemisinin-piperaquine). If the RDT administered during this visit is negative, we will proceed with the blood smear.
  - If the enrolment visit RDT was positive, the blood smear will be expedited.
- If the participant is found to be positive for malaria by microscopy, we will consider the participant ineligible for the cohort and will withdraw him/her. A staff member will return to the house to convey this information and provide second-line antimalarial treatment as per national guidelines (e.g. dihydroartemisinin-piperaquine).

9.1.2.3 *At each monthly cohort visit (starting 4 weeks after enrolment)*

- Prior to each follow-up visit, the cohort study team will call cohort members to remind them of the next visit and reschedule, if necessary, to minimize loss to follow-up. Up to three visits will be made to each cohort study household to complete a follow-up visit.
- At each of these visits, a finger finger-prick blood sample (~250 $\mu$ L to 1mL) will be drawn to prepare approximately five dried blood spots for testing, as indicated in the enrolment visit.
- If the participant has an axillary temperature of  $\geq 37.5^{\circ}$  C or reported history of fever in the last 48 hours, a malaria RDT will be performed using blood from the same fingerprick. Those who test positive for malaria by RDT will be treated at the household according to the Kenya Ministry of Health Guidelines unless they already received appropriate antimalarial treatment from other sources in the previous seven days. Cohort members who do not have objective fevers or report a history of fever in the last 48 hours will not be tested for malaria by RDT.

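### PCR confirmation against lingering HRP2 covers the visit after a treated follow-up event but not the first monthly visit after the artemether-lumefantrine course every child receives at enrolment

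*Protocol*

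**What the plan says.** - **Enrolment (9.1.2.1).** "All cohort members will be treated with artemether-lumefantrine (AL; first-line antimalarial in Kenya) irrespective of their RDT result".
- **First monthly visit (6.3.3.1 and 9.1.2.3).** "The scheduled monthly cohort visits will begin one month after the first day of this treatment"; the heading of 9.1.2.3 gives the same timing: "At each monthly cohort visit (starting 4 weeks after enrolment").
- **Start of counting (9.4.3.1.1).** If the week-2 smear is negative, "person-time accrual will begin two weeks after enrolment to account for the post-prophylactic effect of the full treatment course" of AL. No PCR condition is attached to later events.
- **Treated positive in follow-up (9.4.3.1.2).** The event counts, and two weeks of person-time are removed after each treatment given during follow-up.
- **The visit after that (9.4.3.1.3).** "At the next visit (one month later), if the participant fulfils the criteria for clinical malaria (mRDT positive with symptoms"), the child is treated again, but the episode enters the numerator only if PCR is positive. The reason given is HRP2 "antigenemia which can persist for weeks after active infections have cleared, resulting in false-positive mRDT results".
- **The test (5.1 and 9.3.1).** The primary endpoint accepts "a positive rapid diagnostic test (RDT, pLDH or HRP2"). Section 9.3.1 says the RDTs used in Kenya detect HRP2 and that the main outcomes depend on it.

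**The concern.** The reason for the PCR rule is the interval since treatment of an infection, not whether that treatment was given at enrolment or in follow-up. The first monthly visit is one month after AL, just like the visit the rule covers, and it lies inside counted person-time. A child infected at enrolment may have cleared the parasites, passed the week-2 smear and still carry antigen. If that child has an unrelated fever at the first visit, the RDT can be positive and a primary event is recorded without PCR.

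The primary numerator would then contain events of a kind the protocol itself regards as unreliable. The measured rate rises in both arms. The incidence rate ratio (IRR) is pulled toward 1 only to the extent that enrolment RDT positivity differs less between arms than true incidence does. That is most plausible for children enrolled around first deployment, since later children enrol after exposure to ATSB.

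**Working it through.** **Does the text reach the enrolment course?** Section 9.4.3.1.3 follows directly on 9.4.3.1.2, which concerns treatments during follow-up. Enrolment has its own rule in 9.4.3.1.1, with a smear condition and nothing on PCR. The week-2 procedure in 9.1.2.2 is also informative. A febrile child is re-tested by RDT only if the enrolment RDT was negative; for an enrolment positive the smear is expedited. So at week 2 the protocol does not rely on a repeat RDT after an enrolment positive, but at week 4 such an RDT can define the primary endpoint.

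**The plan's own figures (7.8.1.1).** Inputs: rates λ0 = 0.845 and λ1 = 0.592 per person-year, c = 40 clusters per arm, y = 22 person-years per cluster, CV 0.4, two-sided alpha 0.049 (z = 1.9686).

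- SE² = [(λ0 + λ1)/y + CV²(λ0² + λ1²)]/(c − 1) = (0.0653 + 0.1703)/39, so SE = 0.0777.
- Power = Φ(0.253/0.0777 − 1.9686) = 90.1% (plan: 90%).
- Clusters needed for 90% power: 39.9 per arm (plan: 40).
- Control events: 880 × 0.845 = 743.6 (plan: 744).
- Planned IRR: 0.592/0.845 = 0.701.

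**Size of the gap.** The documents give no cohort enrolment positivity, antigen persistence or unrelated-fever rate. The following are assumptions:

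- p, RDT positivity at enrolment: 34.1%, the pooled all-age survey figure in 7.8.2, used as a proxy.
- q, still antigen-positive at week 4: 20%, 40%, 60%.
- f, unrelated fever at that visit: 5%, 10%, 20%.
- RDT read as HRP2 throughout.

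False events per control child are x = p·q·f. With the average follow-up of five months in 7.8.1.1, the added rate is r = x/(5/12).

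| | Low | Middle | High |
|---|---|---|---|
| x | 0.0034 | 0.0136 | 0.0409 |
| r per person-year | 0.0082 | 0.0327 | 0.0982 |
| r/0.845 | 1.0% | 3.9% | 11.6% |
| r × 880 (events on 744) | 7 | 29 | 86 |

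Let g be the ATSB-to-control ratio of enrolment positivity. Then IRR = (0.592 + g·r)/(0.845 + r), and power comes from the formula above with the inflated rates.

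| g | IRR low / middle / high | Power low / middle / high |
|---|---|---|
| 1 (upper bound) | 0.703 / 0.712 / 0.732 | 89.5% / 87.8% / 82.9% |
| 0.85 | 0.702 / 0.706 / 0.716 | 89.8% / 89.2% / 87.3% |
| 0.775 (= 0.25 × 1 + 0.75 × 0.70) | 0.701 / 0.703 / 0.708 | 90.0% / 89.8% / 89.2% |
| 0.70 | no dilution | no loss |

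**Sensitivity, middle case with g = 1.** With p = 29% or 36.5%, extra events are 3.3% or 4.2% and power is 88.2% or 87.7%. Section 7.8.1.1 does not say whether the planning rate was PCR-confirmed. If 0.845 already contains the false events, the true control rate is 0.845 − 0.0327 = 0.8123 and the counted ATSB rate is 0.8123 × 0.7006 + 0.0327 = 0.6018. The IRR is then 0.6018/0.845 = 0.712 and power is 87.4%.

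**How many visits are unprotected.** 880/(5/12) = 2,112 children per arm, and 2,112 × 0.341 is about 720 first visits after an antigen-positive enrolment. The existing PCR rule covers at most about 744 post-event visits in the control arm, so the uncovered group is of similar size.

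**The case against.** The arithmetic is not in dispute; its weight is. Five points deserve a hearing.

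- **Staggered enrolment.** Most children enrol after ATSB exposure. In the mixed case (g = 0.775) the middle scenario moves the IRR only from 0.701 to 0.703 and power from 90.1% to 89.8%. The 82.9% figure needs equal positivity, 60% persistence and 20% unrelated fever together. This stands, and it is why the effect is called small.
- **Direction.** Values of g below 0.70 are not excluded. With middle inputs, g = 0.6 gives IRR 0.697 and power 91.1%; g = 0.5 gives 0.693 and 91.9%. This stands too: the direction depends on enrolment positivity by arm. A ratio shifted away from 1 by residual antigen is also not wanted.
- **Choice of test.** A secondary cohort endpoint is defined by a pLDH RDT, which suggests that a pLDH read is planned. That would shrink every figure above. But the primary endpoint accepts either antigen, and section 9.3.1 says the main outcomes rely on HRP2.
- **Scope of the wording.** The heading of 9.4.3.1.3 could be stretched to a child who was RDT-positive and treated at enrolment. The order of the subsections and the separate enrolment rule make the narrower reading likelier. At best the text is ambiguous about which primary events count.
- **A matter for the SAP.** Section 9.4.3.1 sets the counting rules itself. Where it leaves something open it says so, as in 9.4.3.1.4: "If a person sleeps outside of their cluster of residence for a period to be defined in the Statistical Analysis Plan". An SAP that follows the protocol would inherit the gap.

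**Conclusion.** The concern holds. The protocol's own reason for PCR confirmation applies equally at the first monthly visit after enrolment treatment, and no other section of the protocol closes the gap there. The existence of the gap follows from the text. Its size does not: it rests on assumed antigen persistence and unrelated fever, on a survey proxy for enrolment positivity, and on an HRP2 read.

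The expected bias is small, and its sign turns on whether ATSB lowers enrolment positivity by less or more than it lowers incidence. This is a cheap correction that should be made; it does not threaten the design.

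A separate point of wording: the one-month reference in 9.4.3.1.3 leaves unclear whether sick visits soon after treatment need PCR confirmation.

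**What to change.** Amend 9.4.3.1.1 and 9.4.3.1.3 so that an RDT-positive febrile illness within a stated window after any AL course counts as a primary event only if PCR on that visit's dried blood spot is positive. The window should include the enrolment course and run at least through the first monthly visit. State that sick visits inside the window are covered, and state which RDT antigen defines the primary endpoint.

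This changes event counting only, not who is tested or treated. No new sampling is needed: blood spots are taken at every monthly and sick visit (9.1.2.3, 9.1.2.4), and PCR on cohort samples is planned for time to first infection (9.3.1). The cost is that some PCR results must be ready before events are counted, including for the interim analyses, and that the event count falls slightly, by about 1% to 4% in the low and middle cases.

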9.4.3.1.5 Missed visits

Missing outcomes due to participant absence at scheduled visits will result in the removal of the previous period of follow-up time. Participants who return to the study after an absence of at least one measurement period and immediately test positive for clinical malaria will not be counted as cases, nor will their follow-up time between the last ascertainment and their return to study be counted (see section 9.4.2.2.1, Missing outcome data, page 46).

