#### 9.4.2.2 Missing data

##### 9.4.2.2.1 Missing outcome data

Significant effort will be made to reduce missing outcome data by revisiting cohort households multiple times and pre-scheduling follow up visits where possible. When missing data does arise due to failed monthly outcome assessment, no imputation will be used. Full reporting of the fraction of missing outcome assessments by study arm will be conducted for the intention-to-treat study population.

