### 9.4.3 Analysis of the primary outcome

#### 9.4.3.1 Definition of events and person-time to obtain incidence rates

The primary outcome analysis will be based on a comparison of the unadjusted (crude) incidence rates between study arms using a multi-level (variance compartments model). The incidence rate will be defined as the total number of incident clinical malaria cases divided by the total person-time observed among each cohort.

The person-time (i.e., the denominator) and events (i.e., the numerator) will be defined as follows:

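### The missed-visit rule drops the interval ending at a return visit, with its event, only when the child tests positive; for a negative child nothing removes it

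*Protocol*

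**What the plan says.** Section 9.4.3.1.5 contains two rules. The first applies to every child: "Missing outcomes due to participant absence at scheduled visits will result in the removal of the previous period of follow-up time". The second applies only to some, namely those that "return to the study after an absence of at least one measurement period and immediately test positive for clinical malaria will not be counted". Besides losing the event, these children lose the time before it: "nor will their follow-up time between the last ascertainment and their return to study be counted".

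Section 9.4.3.1 defines the rate as events "divided by the total person-time observed among each cohort". Section 9.4.2.2.1, to which the missed-visit rule refers, rules out imputation and adds: "Full reporting of the fraction of missing outcome assessments by study arm will be conducted for the intention-to-treat study population". It gives no person-time rule for a child who returns negative.

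Section 9.4.3.1.4 covers nights spent outside the home cluster. There "person-time and events for that month will be excluded", whatever the test shows, with the threshold left to the SAP.

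**The concern.** A rule that removes time at risk should not depend on whether an event was found at the end of that time. Here a positive return visit removes both the event and its interval, while a negative one leaves the interval in the denominator. The rate is pulled downwards.

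The pull grows with the share of intervals that end at a return visit. If that share is the same in both arms, the bias nearly cancels in the incidence rate ratio (IRR), and what remains is an understated incidence in each arm. This still matters for cases averted and for the cost-effectiveness ratio in 9.1.8, which uses clinical malaria incidence. If one arm misses more visits, the IRR shifts in that arm's favour. The trial is open-label (8.2), so unequal attendance cannot be excluded, and the same endpoint drives both interim looks (9.4.1). Reporting missed assessments by arm would reveal an imbalance but would not correct it.

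It is also unclear whether a sick visit between scheduled visits (9.1.2.4) counts as a return.

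**Working it through.** **Reading the rule on one child.** Seen at visit 2, absent at visit 3, back at visit 4.

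| Result at visit 4 | Visits 2–3 | Visits 3–4 | Event |
|---|---|---|---|
| Positive | removed | removed | not counted |
| Negative | removed | no rule removes it | none |

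The first rule treats both children alike. The interval from visit 3 to visit 4 is where they differ.

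**Reproducing the plan's figures (7.8.1.1).** Control events: 0.845 × 880 person-years = 743.6, matching the stated 744. Clusters per arm (Hayes–Bennett), with rates 0.845 and 0.592, 22 person-years per cluster, CV 0.4, two-sided alpha 0.049 and 90% power:

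1 + (z₁ + z₂)² × [(0.845 + 0.592)/22 + 0.4² × (0.845² + 0.592²)] / (0.845 − 0.592)² = 39.9

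This gives the stated 40, with power 90.1%.

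**Inputs for the size of the effect.** From the protocol: control rate 0.845 per person-year, IRR 0.70, six monthly visits. Assumed: 5% or 10% of visits missed; absence unrelated to malaria; a share s of events found and counted at sick visits; a factor k for the number of return intervals (k = 1 if misses are independent, k = 0.5 if consecutive absences, loss to follow-up or the sleeping-away rule halve that number).

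**Formulae.**
- Share of attended visits that follow a missed one: f = k × missed rate × 5/6 (the first monthly visit follows attended enrolment).
- Chance of an event in one interval found only at the scheduled visit: p = 1 − exp(−rate × (1 − s)/12).
- Rate under the literal rule divided by rate under a result-neutral rule: s + (1 − s)(1 − f)/(1 − f·p).

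The correction 1 − f·p is applied only to the scheduled-visit term. Applying it to both terms changes the multipliers by less than 0.002.

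**Worked case** (k = 1, s = 0.5, control misses 5%, ATSB 10%). Control: f = 0.0417, p = 0.0346, multiplier 0.980. ATSB (rate 0.5915): f = 0.0833, p = 0.0243, multiplier 0.959. The ratio is 0.979, so 0.70 becomes 0.685.

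**Results.**

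| k | s | Control incidence understated, 5% / 10% missed | IRR, control 5% v ATSB 10% | IRR, control 10% v ATSB 5% |
|---|---|---|---|---|
| 1 | 0 | 3.9% / 7.8% | 0.670 | 0.729 |
| 1 | 0.5 | 2.0% / 4.0% | 0.685 | 0.715 |
| 1 | 0.75 | 1.0% / 2.0% | 0.693 | 0.707 |
| 0.5 | 0 | 1.9% / 3.9% | 0.686 | 0.714 |
| 0.5 | 0.5 | 1.0% / 2.0% | 0.693 | 0.707 |
| 0.5 | 0.75 | 0.5% / 1.0% | 0.696 | 0.704 |

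With equal missed-visit rates the largest change is at k = 1, s = 0, 10% missed: 0.70 × 0.9204/0.9219 = 0.6988, a shift of 0.0012.

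A simulation of 1.5 million children per arm, applying both rules to the same data with independent misses and the same 5% v 10% gap, gave the same shifts: 0.706 to 0.676 at s = 0, and 0.705 to 0.690 at s = 0.5. Its neutral value is slightly above 0.70 because one visit detects at most one episode; only the shift is due to the rule. With autocorrelated misses (persistence 0.4) the effect was about half, in line with the k = 0.5 rows.

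**The case against.** The strongest reply is that the text is ambiguous rather than wrong: the previous period in the first rule could mean the whole gap up to the return, for everyone. But the person-time clause of the second rule would then be redundant, and its presence suggests that the first rule does not cover that time.

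A second reply is that person-time derivations belong in the SAP. Section 9.4.3.1.4 does defer its threshold there. Section 9.4.3.1.5 defers nothing and fixes the asymmetry itself. The sleeping-away rule is neutral and will catch some of these absences, since travel is asked about at each visit, but it is triggered by nights away and not by a missed visit.

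A third is that false-positive rapid tests justify discarding a positive at return, because of "antigenemia which can persist for weeks after active infections have cleared" (9.4.3.1.3). That may justify not counting the event. It does not justify keeping the matching interval for negatives.

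What stands concerns size. Nothing in the protocol suggests unequal attendance: reminder calls and up to three attempts apply to all cohort households. The s = 0 rows are an upper bound. At monthly visits, children without current fever who do not "report a history of fever in the last 48 hours will not be tested for malaria by RDT" (9.1.2.3), and families are asked to call when a child falls ill, so sick visits should find a good share of episodes. The result-neutral rule is itself unbiased only if absence is unrelated to malaria.

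**Conclusion.** The concern holds as a defect in the stated rule: on its literal wording, one interval enters or leaves the primary rate according to the test result. It should be fixed, but it does not undermine the primary contrast in the expected case. Absolute incidence is understated in both arms by roughly 0.5% to 8% over the assumed range. The IRR is essentially unchanged when missed visits are balanced. With an assumed five-point gap between arms it moves from 0.70 to between 0.670 and 0.696, or between 0.704 and 0.729, favouring the arm that misses more visits. The missed-visit rates, the gap between arms, s and k are all assumptions, so the risk to the IRR is conditional.

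**What to change.** Reword 9.4.3.1.5 so that it does not depend on the test result. For every child who misses one or more scheduled visits, exclude the gap from the last assessment to the return visit, and any event in it or at that visit. Restart person-time at the return visit, less the usual two weeks after any treatment (9.4.3.1.2). State that only scheduled visits open and close a gap.

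Add a sensitivity analysis that keeps the return interval and its event for all returners, with return-visit positives confirmed by PCR as in 9.4.3.1.3.

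The cost is one or two sentences and the matching derivation, with no new data collection. At 5% or 10% missed visits and k = 1, the change removes about a further 3.9% or 7.8% of person-time (0.039 × 880 ≈ 34, or 0.078 × 880 ≈ 69 person-years per arm), and about half that at k = 0.5. Sick-visit events inside those gaps are lost too: s × f, or about 2% / 4% of counted events at s = 0.5 and 3% / 6% at s = 0.75. Their time goes with them, so this costs precision and adds no bias under the same assumption about absence. With 22 person-years per cluster reduced by 3.9% or 7.8%, power falls from 90.1% to 89.8% or 89.4%. The change should be made before any unblinded look, so that nobody has to choose between readings with results in hand.
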